3.9.3 Vital Signs and Other Physical Findings

The following vital signs will be collected at Screening, Baseline, Day 43 (week 6) and Day 84 (week 12):

- Systolic and Diastolic blood pressure (mmHg)
- heart rate (bpm)
- body temperature (°F)
- weight (kg)

Summary statistics will be presented for actual values and change from Baseline values by treatment group.

3.9.4 EEG

EEG is collected at Baseline and Day 84 (week 12). Occipital rhythm, rhythmic theta, rhythmic delta, epileptiform abnormalities, and sleep will be analyzed descriptively. For occipital rhythm, the categories are normal, slow, or absent, with undeterminable as a response option. For rhythmic theta, the categories are <50% or >50%, with undeterminable as a response option. For these discrete variables, frequencies and percentages will be presented by treatment group for each visit. The sleep-related variables, total time of sleep recording in minutes, time asleep in minutes and percent time asleep will be summarized using descriptive statistics for each visit by treatment group.

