3.3.3 Safety Endpoints

- Incidence of adverse events
- Change in clinical laboratory parameters from Baseline to each post-baseline assessment
- Shift in clinical laboratory parameters from Baseline to each post-baseline assessment
- Change in vital sign measurements from Baseline to each post-baseline assessment
- Change in physical exam parameters from Baseline to each post-baseline assessment
- Change in EEG from baseline to the end of treatment
- Change in irritability from ABC-C from Baseline to each post-baseline assessment.
- Clinically important changes in seizure medication from the electronic seizure diary

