4.1.8 EEG

Some of the EEG questions will be combined into one question:

- The 3 back ground questions of mild slowing, moderate slowing and severe slowing will be combined into one questions of Background slowing with 1=Mild, 2=Moderate or 3=severe responses
- The 3 Occipital Rhythm questions of normal for age, slow for age or absent will be combined into one question of Occipital Rhythm with responses of normal for age, slow for age or absent.
- The 2 rhythmic theta questions of <50% of the time and >50% of the time will be combined into one question of Rhythmic theta with responses of 1: <50% of the time or 2: >50% of the time.

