Table 14.3.2.1.2	Shift from Baseline in Clinical Labratory Results: Clinical Chemistry, Safety Set
Table 14.3.2.2.1	Summary of Clinical Laboratory Parameters: Hematology, Safety Set
Table 14.3.2.2.2	Shift from Baseline in Clinical Labratory Results: Hematology, Safety Set
Table 14.3.3	Summary of Vital Signs, Safety Set
Table 14.3.4.1	Summary of EEG: Readability and EEG Background , Safety Set
Table 14.3.4.2	Summary of EEG: Occipital rhythm, Safety Set
Table 14.3.4.3	Summary of EEG: Rhythmic Theta, Safety Set
Table 14.3.4.4	Summary of EEG: Rhythmic Delta, Safety Set
Table 14.3.4.5	Summary of EEG: Epileptiform Abnormalities, Safety Set
Table 14.3.4.6	Summary of EEG: Sleep, Safety Set
Table 14.3.4.7	Summary of Seizures (as Recorded in Diary), Safety Set
Table 14.3.5.1	Summary of Physical Exam Results, Safety Set
Table 14.3.5.2	Shifts from Baseline in Physical Exam Results, Safety Set

7 List of Figures

8 List of Listings

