8. INTRODUCTION

8.1 Background and Overview of Angelman Syndrome

Angelman syndrome (AS) is a rare neurogenetic disorder associated with the deletion of or mutation in the Ubiquitin Protein Ligase E3A gene (*UBE3A*). While expressed ubiquitously in the cells of other tissues, in neurons the paternal allele is preferentially silenced through the epigenetic process known as imprinting. Therefore, any alteration in the maternal copy of *UBE3A* results in the expression of the AS phenotype. The syndrome occurs in approximately 1 in every 15,000 live births and has several distinct characteristics. Clinical findings range in severity and may include developmental delay, movement and/or balance disorder, and tremulous movement of limbs. The most unique behavioral characteristic is the combination of a happy demeanor, smiling, and easily provoked. Moreover, these individuals possess a short attention span and an easily excitable personality exhibited by hand-flapping or waving movements. Finally, individuals with AS suffer from motor dysfunction related to gait and balance, severe disruptions in sleep, impairments in speech, anxiety, and frequent seizures with characteristic abnormal electroencephalogram (EEG) patterns¹.

Current Therapies for Angelman Syndrome

There are no current specific treatments for AS. Clinical management includes management of symptoms including anti-epileptic medications for seizure control and oftentimes medications for sleep or anxiety. Physical and occupational therapies, communication therapy, and behavioral therapies are important in allowing individuals with AS to reach their maximum developmental potential².

Pre-clinical Experience with OV101

Research has shown that absence (or dysfunction) of *UBE3A* results in an aberrant increase in the uptake of gamma-aminobutyric acid (GABA), which is the main inhibitory neurotransmitter in the brain. OV101 is the first highly selective GABA receptor agonist that binds to the α 4 and δ -containing GABA_A receptors. These receptors mediate tonic inhibition and contribute to sleep maintenance. Further, in a mouse model of AS, gaboxadol was shown to restore tonic inhibition in *Ube3a*-deficient cerebellar neurons and correct motor abnormalities in *Ube3a*-deficient mice³.

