15.5 Electroencephalogram Assessments

EEG will be assessed as changes in background rhythms and the frequency of epileptiform discharges. Study centers will perform a routine EEG with local equipment. EEG should be done towards the end of a visit to minimize any confounding impact on subject performance. Standard protocol and montage will be followed as outlined in the separate EEG manual, including but not limited to resting and evoked stimuli. Placing of electrodes (if possible according to the international 10/20 system) must be documented. Recording should last about 10 minutes in the wake state, and if possible, recording should end with a nap period. Data will be collected in electronic format in European Data Format for centralized reading. An EEG manual will be provided.

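### SAP 3.9.4 summarises EEG by visit only: it specifies no summary of discharge frequency and no within-subject change or shift, although protocol 15.5 and SAP 3.3.3 call for them

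*SAP*

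**What the plan says.** Protocol 15.5 describes the assessment: "EEG will be assessed as changes in background rhythms and the frequency of epileptiform discharges". Protocol 9.1 lists EEG among the safety endpoints for the primary objective, and SAP 3.3.3 states the endpoint as "Change in EEG from baseline to the end of treatment".

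The analysis is in SAP 3.9.4: "Occipital rhythm, rhythmic theta, rhythmic delta, epileptiform abnormalities, and sleep will be analyzed descriptively". That section gives response options for occipital rhythm and rhythmic theta, then says "For these discrete variables, frequencies and percentages will be presented by treatment group for each visit". For sleep, "The sleep-related variables, total time of sleep recording in minutes, time asleep in minutes and percent time asleep will be summarized using descriptive statistics", again for each visit. It gives no response scale for epileptiform abnormalities or rhythmic delta.

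SAP 4.1.8 sets out how some EEG questions are merged. The three background-slowing questions "will be combined into one questions of Background slowing with 1=Mild, 2=Moderate or 3=severe responses", and occipital rhythm and rhythmic theta are merged in a similar way. It has no entry for epileptiform findings. In the SAP's list of tables, Table 14.3.4.5 appears as a title only: "Summary of EEG: Epileptiform Abnormalities, Safety Set".

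**The concern.** The protocol names a quantity, how often discharges occur, and both documents speak of change. The SAP's EEG text plans a cross-section at Baseline and another at Day 84. Two cross-sections show whether a group's distribution moved, but not how many subjects got worse. If some subjects worsen and a similar number improve, the by-visit percentages barely differ.

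This matters more here because the protocol describes the syndrome as having "frequent seizures with characteristic abnormal electroencephalogram (EEG) patterns" (protocol 8.1), and exclusion criterion 2 removes only poorly controlled seizures. Some subjects may therefore already have epileptiform findings at Baseline. For them the question is whether the findings become more frequent on drug, and the plan names no summary that answers it.

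**Working it through.** **Plan's own figure.** The documents give no number for EEG. The only design figure is the precision for an adverse event incidence of 25% (protocol 17.1). It reproduces: 1.96 × √(0.25 × 0.75 / 25) = 0.170 and 1.96 × √(0.25 × 0.75 / 20) = 0.190, against the stated 17% and 19%. It is used below only for the group size of 25.

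**Safety domains compared within the SAP.**

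- Laboratory (3.9.2): values and changes from baseline, plus shift tables to each post-baseline time point.
- Vital signs (3.9.3): values and changes from baseline.
- Physical examination (3.9.5): normal and abnormal by visit, plus shifts from baseline to the final visit.
- EEG (3.9.4): by-visit counts and percentages, and by-visit descriptive statistics for sleep times. No change and no shift.

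EEG is recorded at Baseline and Day 84, so each subject with both recordings has a pair. The data for a shift table are already collected.

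**Discharge frequency.** The word for frequencies in 3.9.4 refers to counts of subjects, not to the rate of discharges. No count, rate or grade of discharges is named in 3.9.4, 4.1.8 or the table list.

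**Declaration.** SAP section 1 says that substantial differences from the protocol will be identified. The visible text of 3.11 covers caregiver description, the per-protocol criterion, the ABC-I, hypothesised effects and the primary comparison. It does not mention EEG.

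**Masking by offset.** Let *a* subjects go from absent to present and *b* from present to absent, in an arm of 25. The tabulated percentage moves by (*a* − *b*)/25. With an assumed 80% present at Baseline, 20 are present and 5 absent. If all 5 absent become present and 5 of the 20 become absent, both visits read 20/25 = 80%. A shift table would show 5 worsened and 5 improved.

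**Ceiling, only if the item is present/absent.** Subjects able to worsen per arm = 25 × (1 − baseline prevalence). The prevalence is assumed:

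- 60%: 25 × 0.40 = 10
- 80%: 25 × 0.20 = 5
- 90%: 25 × 0.10 = 2.5

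**Simulation, all EEG inputs assumed.** There were 50 OV101 and 25 placebo subjects and 2,000 runs. Discharge rates were log-normal (median 20 per recording, log SD 0.8) with Poisson counts, and the rate doubled on drug in subjects who already had discharges. The drug group's share with any discharge changed by about 0.1 percentage point. A Fisher test on presence at the end of treatment was significant at 0.05 in 4.05%, 2.75% and 2.65% of runs at 50%, 80% and 90% prevalence. A rank test on within-subject log change in count was significant in 96.85%, 100% and 100%. The SAP plans no EEG test; the comparison only shows how much information each summary carries under these assumptions.

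**The case against.** A reader might infer that an increase in discharges cannot register in subjects who already have them. The documents do not support that. It requires present/absent recording, which is stated nowhere. The visible items point to a form that grades some findings: slowing as mild, moderate or severe, and theta by share of recording time. A graded epileptiform item would let some worsening appear in by-visit percentages. In 3.9.4 the sentence on discrete variables follows directly on occipital rhythm and theta, so even its application to epileptiform abnormalities is a reading. The scale may be set in the separate EEG manual, which is not part of these documents.

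A reader might also infer that EEG is reported only as percentages of subjects. That is wrong, because the sleep times get continuous summaries.

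Other points have weight. SAP 4.1.8 covers only questions that need merging, so its silence on discharges proves little. If a discharge count exists, the general methods (3.1) and the change formula (4.2.1) could be applied to it. The protocol's endpoint list says only EEG, and protocol 17.2 lets the SAP modify its plans. Abnormal EEG is not the same as epileptiform discharge, so the prevalence range has no direct support. Subject listings, the seizure diary table and adverse event tables limit the harm, although none is a planned summary of change in discharges.

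These points remove any claim that the signal is certainly lost. They do not supply the missing summary. A subtraction formula does not define a shift for a categorical item, 3.9.4 asks for by-visit results only, and an unstated scale is itself part of the gap.

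**Conclusion.** The point holds as a gap between the stated endpoint and the planned analysis. Followed as written, SAP 3.9.4 does not produce the change in EEG that SAP 3.3.3 names, specifies nothing for the discharge frequency in protocol 15.5, and leaves the difference undeclared in the visible text of 3.11. This part rests on the wording alone.

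That an increase would go unseen in subjects with discharges at Baseline is conditional on present/absent recording. The figures of 2.5 to 10 of 25 subjects, and the simulation results, are illustrations on assumed inputs and not estimates for this trial. The point is worth correcting before database lock. It does not touch the primary endpoint, the incidence of treatment-emergent adverse events.

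**What to change.** In SAP 3.9.4 and Tables 14.3.4.1 to 14.3.4.5:

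1. State the response scale for epileptiform abnormalities and rhythmic delta as recorded by the central read.
2. Add Baseline-to-Day 84 shift tables by arm for background slowing, occipital rhythm, rhythmic theta, rhythmic delta and epileptiform abnormalities, with the number of subjects who worsened.
3. Where the central read already holds a discharge count or frequency grade, report its within-subject change by arm.
4. Where it does not, record in 3.11 that the protocol's discharge-frequency measure is not analysed.
5. Keep the by-visit percentage tables.

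The cost is SAP wording and a few extra tables from data already collected. Re-reading is not proposed: it could involve up to 75 × 2 = 150 recordings, each with only about 10 minutes of waking EEG made on local equipment.

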3.9.5 Physical Examination

Physical exams will be evaluated by body system. Physical exam data are collected at Screening, Baseline, Day 43 (week 6) and Day 84 (week 12). The number and percentage of subjects in each treatment group with normal and abnormal physical examination results for each body system by visit will be presented. For each body system, shifts from baseline to final visit (no change, normal to abnormal or abnormal to normal) will also be presented.

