| Study Rationale OV101 (gaboxadol) is being evaluated in Phase 2 studies of subjects with AS. This rare neuro-genetic disorder occurs in approximately 1 in every 15,000 live births and manifests as several distinct characteristics. Consistent clinical findings range in severity and include developmental delay, movement and/or balance disorder, and tremulous movement of limbs. Perhaps the most unique behavioral characteristic is the combination of a happy demeanor, smiling, and frequent bouts of laughter. Moreover, these individuals possess an easily excitable personality exhibited by hand-flapping or waving movements. Finally, these individuals suffer from motor dysfunction related to gait and balance, severe disruptions in sleep, impairments in speech, and frequent seizures with characteristic abnormal electroencephalogram (EEG) patterns. Individuals with AS will require life-long care. OV101 is the first highly selective extrasynaptic gamma-aminobutyric acid (GABA) receptor agonist that binds to the α 4 and δ -subunit containing extrasynaptic GABA receptors as an orthosteric agonist and may restore the deficit in tonic inhibition that has been associated with AS. This is unlike any other GABAergic agent, including benzodiazepines, zolpidem and other Z-drugs, neurosteroids and drugs that act on GABA metabolism or uptake. Further, in a mouse model of AS, gaboxadol was shown to restore tonic inhibition in UBE3A-deficient cerebellar neurons and correct motor abnormalities in UBE3A-deficient mice. These results suggest that OV101 may alleviate the motor dysfunction observed in individuals with AS. These potential effects on tonic inhibition may impact motor function in people with AS. Previous Phase 2 and 3 studies in subjects with primary insomnia suggest OV101 is effective in restoring classical sleep parameters and slow-wave sleep, resulting in an improvement in the quality and restorative effects of sleep. One study using a transient insomnia model involving 100 subjects showed that administration of OV101 resulted in statistically significant improvements on both sleep induction and sleep maintenance. More importantly, these effects were achieved without the risk of drug dependence. |

| |
|--|

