15.2 Physical Examination

A physical examination should be performed at each visit to evaluate the medical condition of the subject and detect any sign/symptom of AEs, and to perform all the procedures required per protocol.

A full physical examination will include a relevant general assessment of: head, eyes, ears, nose and throat; neck; heart; chest (including lungs); abdomen; extremities; skin; lymph nodes; as well as neurological and cardiovascular systems.

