17.2.3.2 Safety Variables

The following safety variables will be evaluated:

- SAEs, and TEAEs throughout the study, TEAEs leading to study discontinuation, treatment-related TEAEs, and TEAEs of special interest
- Clinical safety laboratory values at Weeks 6 and 12
- Suicidality (using the ABC-C Irritability subscale) at Weeks 6 and 12
- Vital signs at Weeks 6 and 12
- EEG and seizure diary assessments from baseline to end-of-study
- Physical Exam at weeks 6 and 12

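### The physical-exam shift table in SAP 3.9.5 leaves out the Week 6 change that SAP 3.3.3 calls for, and files every abnormal-to-abnormal subject under no change

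*SAP*

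**What the plan says.** SAP 3.3.3 lists among the safety endpoints "Change in physical exam parameters from Baseline to each post-baseline assessment". SAP 3.9.5 places the post-baseline exams at Day 43 (Week 6) and Day 84 (Week 12) and plans two summaries. The first is by visit: counts and percentages with a normal and with an abnormal result, per body system and arm. The second is within subject, again per body system: "shifts from baseline to final visit (no change, normal to abnormal or abnormal to normal) will also be presented". The corresponding entry in the SAP's list of tables, Table 14.3.5.2, is titled "Shifts from Baseline in Physical Exam Results, Safety Set" and names no visit.

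In the protocol, physical-exam findings are one of the safety endpoints under the primary objective (section 9.1). Section 17.2.3.2 lists "Physical Exam at weeks 6 and 12" as a safety variable. Section 15.2 describes a full examination by body system, "as well as neurological and cardiovascular systems".

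**The concern.** The SAP defines the endpoint as a change to each post-baseline exam but tabulates within-subject change to one exam only. Laboratory results are treated differently: SAP 3.9.2 plans shifts to every post-baseline time point. Week 6 matters because the protocol allows down-titration throughout treatment (section 12.1.3.6). A finding that is present at Week 6 and gone by Week 12 is therefore a realistic pattern.

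The second problem is the label. With three categories, a subject abnormal at baseline and abnormal at the end has nowhere to go but no change, even if the finding is worse or a different one. The neurological system is where this is likely to bite. The protocol synopsis says of Angelman syndrome: "Consistent clinical findings range in severity and include developmental delay, movement and/or balance disorder, and tremulous movement of limbs". Subjects with such signs may be scored abnormal at baseline, and for them the only movement the table can show is improvement. A reader who sees few adverse shifts in that row could take this as evidence of no neurological harm when it partly reflects the scoring.

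**Working it through.** The plan states no figure on this point, so the check is of wording and of what the categories can show.

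**Step 1: endpoint against analysis.** SAP 3.3.3 requires change to two exams, Week 6 and Week 12. SAP 3.9.5 gives shifts to one. The missing piece is the Baseline-to-Week 6 shift.

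**Step 2: list the paths.** With N for normal and A for abnormal at Baseline, Week 6 and Week 12, there are 2 × 2 × 2 = 8 paths. For a subject whose final visit is Week 12:

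| Path | Planned shift to final visit | Shift to Week 6 (not planned) |
|---|---|---|
| N-N-N | no change | no change |
| N-N-A | N to A | no change |
| N-A-N | no change | N to A |
| N-A-A | N to A | N to A |
| A-N-N | A to N | A to N |
| A-N-A | no change | A to N |
| A-A-N | A to N | no change |
| A-A-A | no change | no change |

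Four of the eight paths are labelled no change: N-N-N, N-A-N, A-N-A and A-A-A. The Week 6 column differs from the planned column in four paths (N-N-A, N-A-N, A-N-A, A-A-N). Among these, N-A-N is a transient worsening that the planned table hides. A-A-A stays at no change in both columns, so adding Week 6 does not help it; that path needs its own category.

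**Step 3: do the by-visit percentages fill the gap?** They are marginal counts. If, between Baseline and Week 6, one subject goes from normal to abnormal and another from abnormal to normal, the abnormal count is unchanged although two subjects changed. Within-subject change cannot be recovered from them.

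**Step 4: illustration of the abnormal-to-abnormal problem.** Inputs: n = 25 per arm (SAP 2.2). Two quantities are assumptions that appear nowhere in the documents: w, the share who truly worsen neurologically, set at 20% regardless of baseline status; and b, the share neurologically abnormal at baseline, varied. True worsenings are n × w = 25 × 0.20 = 5.

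- Expected number shown as normal to abnormal: n × (1 − b) × w
- Expected number filed under no change: n × b × w
- Chance that at least one is shown: 1 − [1 − w(1 − b)]^n

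| b | Shown | Filed under no change | Chance at least one shown |
|---|---|---|---|
| 50% | 2.5 | 2.5 | 93% |
| 80% | 1.0 | 4.0 | 64% |
| 90% | 0.5 | 4.5 | 40% |
| 95% | 0.25 | 4.75 | 22% |
| 100% | 0 | 5.0 | 0% |

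The share filed under no change is b itself. The table shows the direction of the problem; it does not estimate its size in this trial.

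**Step 5: which exam is final?** Protocol 10.1.3.4 has early withdrawals undergo a physical examination on the Week 12 schedule. SAP 3.9.5 does not say whether final visit means Week 12 only or the last available exam, so the denominator of the shift table is open.

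**The case against.** The strongest reply is that the harm is caught elsewhere. Protocol 16.1.1.2 requires any detrimental change in the subject's condition to be recorded as an adverse event. Protocol 15.2 gives detection of adverse events as a purpose of the exam. SAP 3.9.1 counts events that worsen after first dose as TEAEs, and TEAE incidence is the primary endpoint named in the protocol synopsis. Dizziness and somnolence are reported separately as events of special interest. Intolerance that leads to down-titration must be documented as an adverse event. All data are listed by subject (SAP 3.1). The Clinical Global Impression scales cover motor sub-domains (protocol 14.1.5), and the protocol's contents list shows further motor assessments whose text is redacted.

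This stands, and it rules out a reading a reader might reach for: that neurological worsening cannot register in this trial. The documents support that only for the shift table, and only for subjects already abnormal in the body system concerned.

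Two further inferences also fail. One is that SAP 3.9.5 conflicts with protocol 17.2.3.2. That section names exams at Weeks 6 and 12 without asking for change or shifts, and the by-visit summary meets it; protocol 17.2.4.1 requires shift tables only for laboratory parameters. The mismatch is inside the SAP. The other is that baseline neurological abnormality is near universal by diagnosis. The synopsis speaks of consistent findings, but protocol 8.1 says only that findings may include movement or balance disorder, although it goes on to describe motor dysfunction of gait and balance without that qualifier. Neither gives a proportion.

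What the objection does not remove: the SAP defines a physical-exam endpoint separate from adverse events, the planned table does not deliver it, and one of its labels covers subjects who may have changed. Listings give no comparison between arms.

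**Conclusion.** The point holds for the table. SAP 3.9.5 omits one of the two within-subject comparisons that SAP 3.3.3 defines, and this rests on the text alone. That abnormal-to-abnormal falls under no change follows by elimination from the three categories. Three of the four paths given that label include at least one abnormal exam.

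That the neurological row is affected most is a reasonable inference from the protocol's description of the syndrome, not a documented fact. No percentage of missed worsening should be reported as a finding: it equals the assumed baseline rate b and also needs worsening to be independent of baseline status. Total blindness of the row would require b = 100%.

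The consequence is moderate. The table is descriptive, no test or decision rule in the visible text depends on it, and the primary endpoint is untouched. It is still worth correcting before database lock, because the table summarises a safety endpoint under the primary objective and could be read as reassurance it cannot give.

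**What to change.** In SAP 3.9.5 and Table 14.3.5.2:

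1. Present shifts from baseline to Week 6 and from baseline to Week 12 or final visit, and state which exam counts as final for subjects who withdraw early.
2. Replace no change with two categories, normal to normal and abnormal to abnormal, alongside the two existing shifts.
3. Add a footnote that abnormal to abnormal does not distinguish stable from worsened findings, and that worsening is captured in the TEAE tables.
4. Optionally, if descriptions of abnormalities are already recorded, have them reviewed blind before lock to split abnormal to abnormal into unchanged and new or worsened.

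Items 1 to 3 use data already collected and cost SAP wording plus a few table rows and columns. Item 4 costs a short blinded listing review and depends on a field the documents do not show. Adding a new field to the case report form is not proposed: SAP 3.9.7 describes what happened in practice during the study, so visits had already taken place when the SAP was written and the field could not be completed prospectively for them.
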